7.1.2 Consolidation therapy phase

Consolidation therapy will consist of up to four cycles of infusional HiDAC and Pembrolizumab (MK-3475) (intervention arm) vs. HiDAC alone (control arm). Patients <60 years of age will receive 3 g/m² every 10-12 hours (Q12H) on Days 1, 3, and 5 (total 6 doses). Patients ≥60 years of age will receive 1.5 g/m² Q12H on Days 1, 3, and 5 (total 6 doses). Cycle 1 of consolidation therapy must start within 4 weeks of documenting remission status. Each cycle lasts ~28 days (up to 42 days). Patients in the intervention arm will continue to receive MK-3475 (pembrolizumab) Q3W (±3 days). Do not administer pembrolizumab concurrently with HiDAC chemotherapy Days 1-5 of each consolidation cycle. For consideration of timing of pembrolizumab, allow at least 3 hours after completion of chemotherapy prior to pembrolizumab

administration. Administration window for pembrolizumab may be extended to allow for this timing as necessary. After Cycle 1 of HiDAC, bone marrow assessment will be performed at the time of count recovery (same rules apply as post induction bone marrow in case of lack of count recovery) for formal assessment of response and MRD. Patients, who remain in CR or CRi, will be allowed to proceed to up to 3 more cycles of HiDAC and Pembrolizumab (MK-3475) (intervention arm) vs. HiDAC alone (control arm). Patients, who are not in CR or CRi will be taken off study. . If Pembrolizumab (MK-3475) is discontinued for any reason (after at least one dose of Pembrolizumab), the patient should continue Consolidation therapy on study.

Consolidation Therapy Regimen Description					
Agent	Premedications ; Precautions	Dose*	Route	Schedule	Cycle Length
Pembrolizumab (MK-3475) (For Intervention Arm only)	Premedication with antipyretic and antihistamine may be considered. No premedication with steroids	200 mg See Section 8.1 for instructions on the preparation of the infusion solution.	IV over 30 minutes (between 25-40 minutes) using an infusion set containing a low-protein binding 0.2 to 5 µm in-line filter. See Section 8.1 for compatible infusion set materials including in-line filter.	Q3W (±3 days) continuous from Day 8 of Induction. For consideration of timing of pembrolizumab, allow at least 3 hours after completion of chemotherapy prior to pembrolizumab administration	28 days (±7 days)

Cytarabine [#]	Premedications/ precautions as per standard local procedures. No specific premedications required. premedication with antipyretic and antihistamine may be considered	3 g/m ² . For patients ≥60 years, dose lowered to 1.5 g/m ² Q12H on Days 1, 3, and 5. Reconstitut ion and diluent s as per standard local	IV over 1-3 hours every 10- 12 hours	Days 1, 3, and 5
-------------------------	--	---	--	---------------------

Consolidation Therapy Regimen Description					
Agent	Premedications ; Precautions	Dose*	Route	Schedule	Cycle Length
		procedures / per package insert. Refer to Section 8.2.1 for additional informatio n.			
*Dose rounding per institutional guidelines is allowed.					

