10 STATISTICAL CONSIDERATIONS

10.1 Study Design/Endpoints

This is an open label, randomized, phase 2 study. The study will consist of an induction, consolidation, and maintenance phase of therapy. A total of 50 patients will be included (25 patients in the intervention arm and 25 patients in the control arm).

Induction chemotherapy for AML has been demonstrated to result in MRD negative CR (not just CR) in about 50% of patients treated (Freeman *et al.*, 2013). Few large data sets of MRD negative CR exist across different subpopulations. We hypothesize that the addition of MK-3475 (pembrolizumab) to induction chemotherapy will lead to a 25% improvement of MRD negative CR/CRi after induction and one cycle of consolidation therapy compared to 7+3 and one cycle of consolidation chemotherapy alone. We expect a response rate of 75% in the intervention arm and 50% in the control arm for patients completing their respective treatments. Using intention-to-treat analysis, in open label study, with 25 patients in the intervention arm and 25 patients in the control arm and a significance level of 0.1, we have approximately 71% power to detect an MRD-negative CR/CRi response rate difference of 25% using a one-sided Z-test for two proportions.

Early safety schedule change: After the first 6 patients have been enrolled on the experimental arm, a safety review committee comprised of the study chair, the PIs of any patient who was enrolled in the experimental arm of the trial, and a representative from CTEP will review the

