10.1.1 Primary endpoint

MRD-negative CR/CRi response rate at time of count recovery after first cycle of consolidation therapy with chemotherapy + Pembrolizumab (MK-3475) vs. 7+3 and one cycle of consolidation chemotherapy alone.

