10.2 Sample Size/Accrual Rate

A total of 50 patients (25 per arm) are planned to be enrolled in the intent-to-treat analysis, which will evaluate a 25% difference in the rate of MRD-negative CR/CRi with ~71% power and an overall, one-sided alpha level of 0.1. All patients being randomized and starting induction therapy should be included in the primary analysis.

PLANNED ENROLLMENT REPORT

Racial Categories	Ethnic Categories				Total
	Not Hispanic or Latino		Hispanic or Latino		
	Female	Male	Female	Male	
American Indian/ Alaska Native	0	0	0	0	0
Asian	1	1	0	0	2
Native Hawaiian or Other Pacific Islander	1	1	0	0	2
Black or African American	1	1	1	1	4
White	15	20	1	2	38
More Than One Race	1	1	1	1	4
Total	19	24	3	4	50

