- h Albumin, alkaline phosphatase, total bilirubin, bicarbonate, BUN, calcium, chloride, creatinine, glucose, LDH, phosphorus, potassium, total protein, SGOT [AST], SGPT [ALT], sodium.

NCI Protocol #: 10300

Version Date: April 10, 2025

- i CBCs (with differential and platelet count), which includes WBC, ANC, platelets, Hgb, and Hct required for protocol therapy must be done <24 hours prior to the treatment cycle.
- j For women of childbearing potential, a serum or urine pregnancy test must be conducted within 72 hours prior to first dose of study treatment on both Arm A and Arm B. If the urine test is positive or cannot be confirmed as negative, a serum pregnancy test will be required.
- k TSH should be performed at baseline and <72 hours prior to each dose of Pembrolizumab (MK-3475). Additional T3 and T4 tests should be performed as clinically indicated, if TSH is abnormal, if symptoms are suggestive of thyroid dysfunction.
- l Bone marrow aspirate is required to be submitted for central MRD testing as outline in Section 5. Submit to [name] lab at Children's Hospital Los Angeles. Results will be forwarded to the submitting institution within 1-2 business days of receipt of the bone marrow aspirate samples. Local bone marrow biopsy (aspirate) must be performed at the indicated time points and should follow the institutional standard of care.
- m To be collected between Day 14 and Day 21.
- n To be collected between Day 28 and Day 42.
- o To be collected at the end of consolidation therapy only.
- p Bone marrow aspirations every 3 months during maintenance/observation phase are optional and should only be collected when part of standard of care.
- q To be collected every 3 months during maintenance phase.
- r Blood collection for the immune cell subset analysis and Olink assay only.
- s Bone marrow aspiration and blood should be collected for MRD status in patients who have not relapse. For patients who have relapsed, bone marrow core biopsies, bone marrow aspirate, and blood should be collected. Blood collection for cfDNA will be obtained at the same time-points as blood collection for MRD status.
- t Repeat TTE should be performed before 5+2 reinduction.
- u PT, PTT, and fibrinogen will be additionally collected on days 8 and 9 (pre- and post-) in the pembrolizumab arm.

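### The study calendar puts the primary-endpoint marrow at Day 28 ± 3, while Sections 7.1.2 and 10.1.1 put it at count recovery

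*Combined protocol and SAP*

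**What the plan says.** Section 10.1.1 defines the primary endpoint as the "MRD-negative CR/CRi response rate at time of count recovery after first cycle of consolidation therapy". The treatment text in Section 7.1.2 agrees: "After Cycle 1 of HiDAC, bone marrow assessment will be performed at the time of count recovery". It adds that the post-induction rules apply if counts do not recover. Section 7.1.1 gives those rules:

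- Count recovery means platelets above 50,000 or neutrophils above 500.
- Without recovery, a marrow is due by Day 42.
- If that marrow is hypoplastic and counts are still low, it is repeated every 2 weeks (± 3 days) until recovery or persistent AML.

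The study calendar (Section 12) differs. In the block that holds the marrow rows, the consolidation Cycle 1 marrow sits under D28, a column marked with footnote β (3 days either side). The induction marrow carries footnote n, "To be collected between Day 28 and Day 42". The consolidation Cycle 1 marrow does not carry footnote n, and nothing in its entry refers to count recovery or to a repeat.

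Cycle length is also stated twice. The text of 7.1.2 says "Each cycle lasts ~28 days (up to 42 days"; the regimen table in the same section gives 28 days plus or minus 7.

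Under Section 10.5.2, a patient not in CR or CRi after first consolidation counts as a treatment failure. Under 7.1.2 that patient also leaves the study.

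**The concern.** One marrow decides the primary endpoint, and the protocol gives it two timings without saying which governs. The calendar allows for slow recovery after induction but not at the marrow that matters most for the analysis. Sites often schedule from the calendar. A sample taken on a fixed day, before counts recover, may fall into a response category that does not count as success even though the leukaemia is in remission. With 25 patients per arm, a few such patients would be visible in the result.

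**Working it through.** **1. The two windows**

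| Source | Time of the consolidation Cycle 1 marrow |
|---|---|
| 10.1.1 and 7.1.2 | At count recovery; first marrow no later than Day 42 if unrecovered; repeats every 2 weeks while hypoplastic and unrecovered |
| Section 12, D28 with β | 28 − 3 = Day 25 to 28 + 3 = Day 31 |

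The latest first marrow differs by 42 − 31 = 11 days. The cycle-length statements differ as well: a maximum of 42 days against 28 + 7 = 35 days.

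**2. What happens to a pre-recovery sample**

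An unrecovered patient has platelets at or below 50,000 and neutrophils at or below 500. Both are under the CR thresholds of 100,000 and 1,000 (13.2.2). Suppose the marrow is free of blasts.

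- *Hypoplastic marrow, 7.1.2 followed:* the marrow is repeated. The early sample does not settle the outcome.
- *Hypoplastic marrow, site works from the calendar alone:* the calendar does not mention the repeat, so it may not be done.
- *Marrow not hypoplastic:* the repeat rule does not cover this patient. CRi (13.2.3) excuses residual neutropenia *or* thrombocytopenia. If that means one lineage only, the patient is MLFS (13.2.6), which is a separate category, and 10.5.2 scores a failure. If it allows both, the patient can be CRi.

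**3. How common this could be**

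The documents give no recovery times for this regimen. The general cytarabine information in Section 9.2.1 lists a second neutrophil recovery at 24 to 34 days, which runs past Day 31, but platelet recovery at 15 to 25 days. One lineage is enough for recovery. Taken at face value, the platelet figure puts recovery at or before Day 25, the first day of the calendar window.

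**4. The plan's own power figure**

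Inputs: 25 per arm (10.1, 10.2); "We expect a response rate of 75% in the intervention arm and 50% in the control arm" (10.1); "an overall, one-sided alpha level of 0.1" (10.2); "using a one-sided Z-test for two proportions" (10.1). Section 10.1 states "we have approximately 71% power to detect an MRD-negative CR/CRi response rate difference of 25"%.

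Power = Φ[(d − z × s0) / s1], where d = p2 − p1, p̄ is the mean of the two rates, s0 = √(2p̄(1 − p̄)/n), s1 = √((p1(1 − p1) + p2(1 − p2))/n) and z = 1.2816.

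- p̄ = 0.625; s0 = √0.01875 = 0.1369; s1 = √0.0175 = 0.1323.
- (0.25 − 1.2816 × 0.1369) / 0.1323 = 0.563, so power is 71.3%.
- Summing the binomial probabilities over all outcomes that this test rejects gives exact power 70.9%.

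The stated figure reproduces.

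**5. Illustration of a loss equal in both arms**

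Let m be the share of true responders permanently scored as failures. This is an assumption; the documents give no value. Each rate is multiplied by (1 − m).

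| m | Rates | Normal approximation | Exact power |
|---|---|---|---|
| 0 | 50% vs 75% | 71.3% | 70.9% |
| 5% | 47.5% vs 71.25% | 67.1% | 67.0% |
| 10% | 45% vs 67.5% | 63.0% | 63.3% |
| 20% | 40% vs 60% | 55.4% | 56.1% |

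At m = 10% the expected number misclassified is 0.1 × 25 × 0.50 = 1.25 in control and 0.1 × 25 × 0.75 = 1.875 with pembrolizumab, about three patients in all. If the true rates are equal, an equal loss leaves them equal, so this scenario costs power and does not create a false effect.

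**The case against.** The strongest reply is that the governing text is clear and consistent. Sections 7.1.2 and 10.1.1 both say count recovery, and Section 5.1 lists the specimen only as post Cycle 1, with no day. Footnote β is a column window shared with Cycles 2 to 4, not a marrow rule, and an earlier calendar block shows D28 without it. Footnote z ties the stool sample to the marrow collection rather than to Day 28. On this view a site samples early only if it disregards 7.1.2. That limits the consequence. It does not remove the contradiction, because no passage ranks the text above the calendar.

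Three stronger inferences are tempting, and the documents do not support them.

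- *That a hypocellular, unrecovered patient is lost.* The repeat rule covers exactly that patient. The gap is an unrecovered patient whose marrow is not hypoplastic, or one for whom the rule is not applied.
- *That an early sample is necessarily a failure.* This needs the one-lineage reading of CRi. The separate MLFS category favours that reading, but 13.2.4 lets a patient be both CRi and CRh, so it is not settled. The ambiguity would outlast a calendar fix: a patient sampled just as one lineage passes the recovery trigger can still be below both CR thresholds.
- *That the result is biased between arms.* A 10% loss confined to the pembrolizumab arm would give 49% power; confined to control with both true rates at 50%, it would give an exact one-sided false-positive rate of 0.18 instead of 0.10. Both arms share the same consolidation cytarabine and calendar, and no passage gives recovery times by arm. These figures describe a scenario, not this trial.

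It is also fair to say that cycle length concerns treatment scheduling and does not itself time the primary marrow.

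**Conclusion.** The contradiction on the timing of the primary-endpoint sample is certain, and the calendar entry is wrong as written. A site that follows the calendar and not 7.1.2 could sample before count recovery. A blast-free patient with both lineages low could then be classed as MLFS and scored as a failure, provided that CRi is read as one lineage only and that the repeat rule does not cover the patient or is not applied.

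The number affected cannot be derived from the documents and may be small. The fall from 71% to 63% rests on an assumed 10% loss in both arms and on every early sample being a permanent failure, so it shows scale and is not an estimate. No differential bias and no type I error inflation is shown. Severity is minor.

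**What to change.** Add a footnote to the consolidation Cycle 1 marrow and MRD entries in the calendar so that their timing matches the endpoint definition in 10.1.1 and the existing rule in 7.1.2, including the latest day and the repeat rule, identically in both arms. State in 10.1.1 or 10.5.2 that a marrow taken before count recovery does not by itself score the primary endpoint when the repeat rule applies.

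The two consolidation cycle-length statements in 7.1.2 must also be reconciled; no view is taken here on which is right.

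The cost is a calendar footnote, one sentence in the statistical section and the cycle-length correction. No procedure is added beyond those 7.1.2 already requires, and the sample size of 50 and the stated power of about 71% do not change.

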7.1.3 Maintenance therapy phase

Following count recovery from the last cycle of consolidation therapy, a bone marrow biopsy will be performed to assess for response and MRD. Patients, who remain in CR/CRi will continue on maintenance therapy while patients who do not remain in CR/CRi will be taken off study. Patients in CR/CRi will proceed with single-agent Pembrolizumab (MK-3475) (intervention arm) vs. no maintenance therapy (control arm) Q3W dosing schedule for up to 2 years, calculated from first day of maintenance therapy, according to their original randomization (*i.e.*, there will be no second randomization). For patients randomized to Arm B, Pembrolizumab (MK-3475) will be administered on Day 1 (+/- 3 days) of each maintenance cycle (each maintenance cycle is 21 days). Bone marrow samples will be obtained every 3 months while

patients are receiving maintenance or in observation to assess for MRD. Patients, who are deemed to require HSCT, can forgo any remaining protocol-defined consolidation or maintenance therapy and proceed with HSCT. Patients proceeding with HSCT will be followed for survival and SAEs through the first 100 days post-HSCT including assessment for occurrence of acute and chronic GVHD.

Maintenance Therapy Regimen Description					
Agent	Premedications ; Precautions	Dose	Route	Schedule	Cycle Length
pembrolizumab (MK-3475) (For Intervention Arm only)	Premedication with antipyretic and antihistamine may be considered. No premedication	200 mg See Section 8.1 for instructions on the preparation of the infusion	IV over 30 minutes (between 25-40 minutes) using an	Day 1(+/- 3 days) of each 21-day maintenance cycle	21 Days

Maintenance Therapy Regimen Description					
Agent	Premedications ; Precautions	Dose	Route	Schedule	Cycle Length
	with steroids	solution.	infusion set containing a low-protein binding 0.2 to 5 µm in-line filter. See Section 8.1 for compatible infusion set materials including in-line filter.		

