The [name] Lab is working with TwinStrand (a University of Washington “spin off”) to use DS to sequence mutations in acute and chronic leukemia (Araki *et al.*, 2016). This team has carefully selected a panel of 25 genes with the most common point mutations, insertions, deletions, fusions, and duplications associated with AML. They have developed probes targeting whole genes (*e.g.*, *RUNX1*, *TP53*, *etc.*) or specific mutational hotspots (*e.g.*, *FLT3* point mutations and internal tandem duplications (ITD), *NPM1* insertions, *etc.*). These genes are covered by a ~40 kilobase (kb) panel which comprises a median of 99% of all AML-associated mutations within the selected genes. A ~30 kb panel of genes will be used. Sequencing to a depth of 20,000x is expected to provide a 98% power to detect an allele frequency of 0.02% (1 in 5000) and 86% power to detect alleles at 0.01% frequency (see Figure 2, below).

Patients with AML will have DS performed on the bone marrow (BM) and PB at the time of study entry,

at Day 14, at the end of induction therapy (EOI), after one cycle of consolidation therapy, and at the end of consolidation therapy (EOC), and at end of maintenance therapy/observation period for patients who do not progress. For patients who are willing to have BM done every 3 months during follow up, DS in BM and PB could be assessed during maintenance therapy/observation period.

Figure 2. Sensitivity of Duplex Sequencing is a function of input DNA quantity and sequencing depth. Low-level mutations can be detected reliably at 20,000x based on statistical modeling

(Unpublished Data).

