	
 • 8-10 mL blood in Streck tube (mandatory) 	[name] laboratory, Fred Hutchinson Cancer Research Center
	
 • 1 bone marrow biopsy core (processed to FFPE blocks) (mandatory) • 16 mL bone marrow aspirate sent unprocessed in EDTA tubes (mandatory) • 30 mL blood in sodium heparin Green top vacutainer tubes (mandatory) 	EET Biobank

Maintenance therapy/observation phase – Every 3 months (±7 days)

	
 • 10 mL bone marrow aspirate (optional – only if patients have a standard-of-care biopsy that coincides with this collection time point.) • 10 mL blood in EDTA lavender top vacutainer tube (mandatory) 	[name]'s lab, Children's Hospital Los Angeles
--	---	--

	
 8-10 mL blood in Streck tube (mandatory) 	[name] laboratory, Fred Hutchinson Cancer Research Center
After 6 months of Treatment		
	
 1 bone marrow biopsy core (processed to FFPE blocks) (optional) 16 mL bone marrow aspirate sent unprocessed in EDTA tubes (optional) 30 mL blood in sodium heparin Green top vacutainer tubes (mandatory) 	EET Biobank
After 1 year of Treatment		
	
 1 bone marrow biopsy core (processed to FFPE blocks) (optional) 16 mL bone marrow aspirate sent unprocessed in EDTA tubes (optional) 30 mL blood in sodium heparin Green top vacutainer tubes (mandatory) 	EET Biobank
Relapse		
	
 1 bone marrow biopsy core (processed to FFPE blocks) (optional) 16 mL bone marrow aspirate sent unprocessed in EDTA tubes (mandatory) 30 mL blood in sodium heparin Green top vacutainer tubes (mandatory) 	EET Biobank
End of maintenance/observation phase*		
	
 10 mL bone marrow aspirate (mandatory) 10 mL blood in EDTA lavender top vacutainer tube (mandatory) 	[name]'s lab, Children's Hospital Los Angeles
	
 8-10 mL blood in Streck tube (mandatory) 	[name] laboratory, Fred Hutchinson Cancer Research Center

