To compare cfDNA to both DS-based and MFC serial assessment for relapse prediction, separate multivariate models will be developed for each method. Relapse will be modeled as a time-to-event endpoint and Cox regression will be used to assess the association of ctDNA based MRD with this outcome. In the SWOG study, S0106 for newly diagnosed adult AML, MRD status by MFC was a strong predictor of survival, yet MRD predicted relapse-free survival with a poor c-statistic of 0.58.¹ We hypothesize that DS will lead to an improvement in prediction accuracy of relapse-risk (c-statistic 0.85). Assuming MRD-negativity (among CR/CRi) ratios of 1, 3, 0.3, and 0.45 for intensive chemo, intensive chemo + Pem, Aza + Ven, and Aza + Ven + Pem arms, respectively, and a correlation coefficient (ρ) between MFC and DS assays of 0.75 (based on MFC and NGS comparison data),²⁹ a minimum total sample size of 16, 24, 20, and 18 evaluable patients with CR/CRi would provide 80% power to detect a between-arm differencing based on a comparison of two proportional hazards survival curves with one-sided type-I error of 10% without correction for the multiplicity of endpoints: TTR; DFS; and OS.

10.4.2.2 Assessment of immune cell subsets and its correlation with the response to combine chemotherapy and anti PD-1 directed therapy

We will possibly have limited number of cells in the BM aspirate. Therefore, we will analyze the immune profile combining a high-throughput technique that will allow us to study more than 20 markers in a single cell analysis using mass cytometry (CyTOF). These techniques will provide information about the architecture of the tumor microenvironment (TME) (*i.e.*, BM) and the distribution of markers of interest detected with CyTOF. CyTOF-based single cell analysis is a new technology that combines flow cytometry with metal-conjugated antibodies detected by mass spectrometry permitting higher order multiplexing (up to 100 molecules) on a single cell analysis (Bendall *et al.*, 2011). Additionally, after fixation and permeabilization, cells will be stained with anti-human Ki-67-151Eu (B56; BD Pharmingen Ab conjugated with lanthanide MaxPar Europium Chloride 151Eu using the MaxPar X8 Ab labeling kit) for 30 min at room temperature. Cells will be acquired on CyTOF 2 instrument (DVS; Fluidigm Sciences). All data will be analyzed and graphs generated using the DVS Cytobank software (Cytobank).

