The Kaplan-Meier method and log-rank test will be used to estimate the distribution of survival between/among different marker strata. Univariate or Multivariate cox proportional hazard models will be employed to explore the significance of biomarkers on survival outcomes, while adjusting for the potential prognostic factors. The interaction effects between treatment and biomarkers also will be evaluated. Serial measurements of biomarkers will be estimated at baseline, end of induction, post-consolidation cycle 1 and 4, every 3 months during maintenance, one year, and end of treatment when applicable. Landmark analysis (Benjamini *et al.*, 1995, Dafni *et al.*, 2011) or joint modeling (Huang *et al.*, 2016) will be used to assess serial measurements of biomarkers dynamical impacts on survival outcomes, where appropriate.

Part 3: Compare the biomarkers effects between treatment arms, intensive chemo + pembro vs. intensive chemo only.

The associations between treatment arms and baseline biomarkers will be evaluated using Chi-squared test/ Fisher's exact test, ANOVA, and the Mann-Whitney U tests as appropriate. Trajectory trends of the changes in markers' values or status across the measurement time will be explored using generalized linear mixed models. The bar plots and trajectory time plots will visually show the differences over time between treatment arms. The associations between markers and the demographic/prognostic factors will also be assessed using the similar statistical methods.

Part 4: Evaluate the correlations between biomarkers.

The correlations between biomarkers will be evaluated using Pearson/Spearman rank-order correlation coefficients, Chi-squared/Fisher's exact tests, and Wilcoxon rank sum / Kruskal-Wallis tests as appropriate. A scatter plot, boxplot, and mosaic plot will also be generated for visualization. The multiplicity of the endpoints will be adjusted using the correction of Benjamini and Hochberg (Benjamini *et al.*, 1995).

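### Quarterly marrow in maintenance is required in one section and optional in others, and the exploratory cfDNA versus DS versus MFC relapse comparison does not say how to handle the resulting unequal sampling

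*Combined protocol and SAP*

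**What the plan says.** Four places in the combined protocol and SAP describe marrow sampling in maintenance or observation.

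- Section 7.1.3: "Bone marrow samples will be obtained every 3 months while" patients receive maintenance or are observed, to assess MRD. No optional wording is attached.
- Section 5.1, 3-monthly row: the 10 mL aspirate is optional, "only if patients have a standard-of-care biopsy that coincides with this collection time point".
- Section 12, footnote p: "Bone marrow aspirations every 3 months during maintenance/observation phase are optional and should only be collected when part of standard of care".
- Section 2.5.2: "For patients who are willing to have BM done every 3 months during follow up, DS in BM and PB could be assessed" during this phase.

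Blood is treated differently. Section 5.1 makes both the Streck tube for cfDNA and the EDTA tube mandatory every 3 months. Section 5.8 lists DS on EDTA blood and on cfDNA as mandatory at that interval, and calendar footnote s puts cfDNA blood and MRD blood on the same time points.

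On analysis, section 10.4.2.1.2 states: "To compare cfDNA to both DS-based and MFC serial assessment for relapse prediction, separate multivariate models will be developed for each method". Relapse is a time-to-event outcome in Cox models, and the hypothesis is framed as a c-statistic. Separately, Part 2 of the biomarker plan (under section 10.4.2.8) lists serial biomarker values that include "every 3 months during maintenance", when applicable, to be related to survival outcomes by landmark analysis or joint modeling.

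**The concern.** A site that follows section 7.1.3 takes a marrow at every quarterly visit. A site that follows section 5.1 or footnote p may take none until the end of the phase. Under the optional reading, the marrow series is irregular and may be informative, because whether a marrow exists depends on a decision made outside the protocol. The cfDNA series is complete by design. Separate models fitted to series with different coverage compare sampling schemes as well as assays.

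Section 2.5.2.2 presents the cfDNA work as a test of whether it predicts relapse more accurately than current MRD methods. What is at stake is whether an observed difference can be credited to the assay.

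**Working it through.** **Side-by-side reading.** There is no stated figure to reproduce, because the point does not depend on sample size, power or alpha. Section 7.3 allows up to 2 years of maintenance, so there are 24 / 3 = 8 quarterly visits.

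| Specimen in maintenance | Section 7.1.3 | Section 5.1 and footnote p |
|---|---|---|
| Marrow for MRD | obtained at all 8 | mandatory at none of the 3-monthly points |
| EDTA blood (DS) | not addressed | mandatory at all 8 |
| Streck blood (cfDNA) | not addressed | mandatory at all 8 |

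The end-of-maintenance marrow in section 5.1 is mandatory, but only for patients who do not progress. Under section 5.1, a patient who relapses during maintenance therefore need have no marrow MRD sample after end of consolidation, although quarterly blood is due throughout.

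**Which assays are exposed.** Section 5.9.3 names only marrow for MFC. Section 6.1 names marrow and blood for DS. The fallback to blood in section 5.1 is written for required time points. However, section 5.8 says the EDTA blood goes on for DS after flow studies are complete, so flow on blood may be intended. The specimen behind serial MFC is therefore unclear. Section 10.4.2.1.1 does plan a paired test of DS against MFC for detection, but the relapse-prediction comparison has no equivalent rule.

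**Illustration 1: marrow missed at random.** The assumptions, none of them from the documents, are two identical error-free assays, relapse uniform over months 3 to 24, MRD detectable for a fixed lead before relapse, and marrow taken at each visit with probability q. If f1 and f2 are the fractions of relapses with one or two visits inside the lead window, the share preceded by a positive test is f1·q + f2·[1 − (1 − q)²].

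- 2-month lead: f1 = 14/21, f2 = 0
- 4-month lead: f1 = 15/21, f2 = 6/21
- 6-month lead: f1 = 3/21, f2 = 18/21

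| Lead | q = 1 | q = 0.75 | q = 0.5 | q = 0.25 |
|---|---|---|---|---|
| 2 months | 67% | 50% | 33% | 17% |
| 4 months | 100% | 80% | 57% | 30% |
| 6 months | 100% | 91% | 71% | 41% |

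For example, with a 4-month lead and q = 0.5, the share is 0.714 × 0.5 + 0.286 × 0.75 = 0.571. Simulation of 200,000 relapses agrees with the table to within 1 percentage point. Here marrow looks worse than an identical assay on scheduled blood.

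**Illustration 2: marrow taken more often before relapse.** The assumptions, again not from the documents, are 6% relapse per quarter, 50% sensitivity in the quarter of relapse and 5% false positives.

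- Scheduled blood: PPV = (0.06 × 0.5) / (0.06 × 0.5 + 0.94 × 0.05) = 0.030 / 0.077 = 0.39. Relapses flagged: 50%.
- Marrow at 20% of routine and 80% of pre-relapse visits: PPV = 0.024 / (0.024 + 0.0094) = 0.72. Relapses flagged: 0.8 × 50% = 40%.
- Marrow at 10% and 90%: PPV = 0.027 / (0.027 + 0.0047) = 0.85.
- Marrow at 50% and 90%: PPV = 0.027 / (0.027 + 0.0235) = 0.53.

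With the same assay and the same patients, 20%/80% sampling makes marrow look better on PPV and worse on the share of relapses flagged. Neither measure is the planned Cox or c-statistic analysis. The two illustrations show that unequal sampling alone can separate equal assays, and that the sign depends on the sampling mechanism and the metric.

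**The case against.** The strongest reply is that the comparison is mostly sound and the problem narrow. Much of this stands.

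- Blood DS and cfDNA share one mandatory quarterly schedule, so that comparison is matched through maintenance. A reader might infer that the whole cfDNA, DS and MFC comparison fails. The documents do not support that: the exposed part is marrow-based MFC and marrow-based DS in maintenance.
- Marrow and cfDNA blood are both mandatory at end of induction, after consolidation cycle 1 and at end of consolidation, so a fair comparison is available there.
- A reader might infer that maintenance marrows are triggered by suspected relapse, so that marrow will look more predictive. The text says only standard of care coinciding with a scheduled time point (±7 days), which includes routine surveillance. The relapse row in section 5.1 sends samples to the biobank and lists none for the flow laboratory. A marrow prompted by suspicion could still fall inside the window, so informative sampling is possible but not established.
- A reader might also infer that open-label care leads to different marrow rates by arm. No passage gives such rates, and the analysis in question is between assays.
- Section 10.4.2.1.2 does not itself name maintenance time points. The 3-monthly values are listed in Part 2, which compares no MRD assays and already allows landmark analysis.

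The reply does not remove the conflict between sections 7.1.3, 5.1, 2.5.2 and footnote p. Nor does it supply the missing specimen and pairing rule for an analysis described as serial.

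**Conclusion.** The point holds in limited form. The sections on maintenance marrow contradict each other and must be reconciled. The documents do not settle which schedule is right, and this review does not choose one. If marrow stays optional, the separate-model comparison of marrow-based MFC or DS with cfDNA can show a difference between equally good assays, with coverage of the quarterly visits anywhere from 0 to 8 of 8. Neither the direction nor the size can be determined from the documents. The percentages and PPVs above rest wholly on assumed inputs.

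The analysis is exploratory (objectives 1.3.1 and 1.3.7). The primary endpoint uses a mandatory marrow after consolidation cycle 1 and is not affected.

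**What to change.** 1. Reconcile sections 7.1.3, 5.1, 2.5.2 and calendar footnote p so that one status for the 3-monthly marrow applies throughout. Read literally, section 2.5.2 also makes blood DS conditional on willingness, which conflicts with sections 5.1 and 5.8; settle that at the same time.
2. In section 10.4.2.1.2, name the specimen (marrow or blood) for each of MFC, DS and cfDNA.
3. If marrow stays optional, compare marrow-based MFC and DS with cfDNA only on paired samples from the same patient and time point. Use landmark analysis at end of induction, post consolidation cycle 1 and end of consolidation, and fit the models to the same patients.
4. Keep blood DS versus cfDNA on the full mandatory quarterly schedule through maintenance, so that the longitudinal aim is preserved.
5. Report optional maintenance marrow MRD descriptively, and record why each marrow was taken.

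The cost is mainly wording, plus one data item for the reason. The small downside is that unpaired or optional maintenance marrows leave the head-to-head comparison. The primary analysis and the sample size do not change.
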